**Table 11-3 Acceptable Methods of Contraception**

	Male Subjects and Their Female (Non-study) Partners	Female Subjects and Their Male (Non-study) Partners
Vasectomy performed at least 6 months previously, with a documented negative postvasectomy semen analysis for sperm	Yes	Yes
Bilateral tubal occlusion (e.g., ligation) performed at least 6 months previously	Yes	Yes
Male or female condom with or without spermicide a	Yes	Yes
Female barrier contraception (such as diaphragm, cervical cap, or sponge) with spermicide	Yes	Yes
Continuous use of an intrauterine device for at least 90 days before the first dose of study drug		
Hormone-releasing	Yes	Nob
Non-hormone releasing	Yes	Yes
Hormonal contraceptives, if successfully used for at least 60 days before the first dose of study drug	Yes	Nob

a A female condom cannot be used with a male condom due to risk of tearing.

b **Hormone-releasing** intrauterine devices and **hormonal** contraceptives are not considered an acceptable method in female study subjects due to potential induction of metabolism by VX-659; however, female subjects are not required to discontinue their use of hormone-releasing intrauterine devices or hormonal contraceptives.

**Additional notes:**

- If over the course of the study the subject meets the criteria for waiving the contraception requirements, the subject does not need to follow the contraceptive methods listed in [Table 11-3](#).
- Male subjects must not donate sperm during the period starting from the first dose of study drug until 90 days after the last dose of study drug.
- Female subjects should not nurse a child during the period starting from the first dose of study drug until 90 days after the last dose of study drug.
- For male subjects with a female partner of childbearing potential, the couple should not plan to become pregnant during the study or within 90 days after the last dose of study drug, with the exception of couples who plan to become pregnant by artificial insemination using sperm banked by the male subject before the first dose of study drug or sperm from another source.

**11.7.7.2 Pregnancy**

Subjects will be counseled to inform the investigator of any pregnancy that occurs during study treatment and for 90 days after the last dose of study drug.

If a female subject becomes pregnant during study participation, study drug will be permanently discontinued immediately. The investigator will notify the medical monitor and Vertex GPS within 24 hours of the site's knowledge of the subject's (or partner's) pregnancy using the Pregnancy Information Collection Form. Male subjects with female partners who become pregnant during the study must use a male condom to avoid exposure of a potential embryo or fetus to study drug via the seminal fluid.

If confirmed to be on active drug, the subject or partner will be followed until the end of the pregnancy and the infant will be followed for 1 year after the birth, provided informed consent is obtained. A separate ICF will be provided to explain these follow-up activities. Pregnancy itself does not constitute an AE.

**12 STATISTICAL AND ANALYTICAL PLANS**

This section presents a summary of the planned analyses for this protocol. Statistical analysis details will be provided in the statistical analysis plan (SAP), and clinical pharmacologic analysis details will be provided in the clinical pharmacology analysis plan (CPAP), both of which will be finalized before the clinical data lock for the study and treatment unblinding.

**12.1 Sample Size and Power**

Approximately 360 subjects will be enrolled and randomized (1:1) to the VX-659/TEZ/IVA arm or the triple placebo arm. This sample size was determined to provide adequate power for the key secondary endpoint of number of PEx through Week 24. Information regarding the powering of primary and key secondary endpoints is provided below.

**Power for Primary Efficacy Endpoint**

The primary efficacy endpoint is the absolute change in ppFEV1 from baseline at Week 4. The primary null hypothesis to be tested is that the mean absolute change in ppFEV1 from baseline is the same for the 2 treatment groups, VX-659/TEZ/IVA and placebo. If the number of subjects

included in the IA is 140, the null hypothesis will be tested at a 2-sided significance level of 0.044 during the IA and at an overall 2-sided significance level of 0.05.

Assuming a within-group SD of 7 percentage points and a 5% dropout rate at Week 4, an IA sample size of 70 subjects in each treatment group will have approximately 98% power to detect a difference between the treatment groups of 5.0 percentage points for the mean absolute change in ppFEV1 from baseline at Week 4, based on a 2-sided, 2-sample *t*-test at a significance level of 0.044. If the *P* value fails to cross the efficacy boundary during the IA (*P* value  $\geq 0.044$ ; assuming 140 subjects included in the IA), the primary endpoint of absolute change in ppFEV1 from baseline at Week 4 will be tested after all subjects complete study participation at an alpha of 0.01. A final analysis sample size of 180 subjects in each treatment group will have approximately 99% power to detect a difference between the treatment groups of 5.0 percentage points for the mean absolute change in ppFEV1 from baseline at Week 4, based on a 2-sided, 2-sample *t*-test at a significance level of 0.01. All power calculations were based on EAST software Version 6.4.

### Power for Selected Key Secondary Endpoints

A key secondary endpoint is the absolute change in ppFEV1 from baseline through Week 24. Assuming a within-group SD of 7 percentage points and a 10% dropout rate at Week 24, a sample size of 180 subjects in each treatment group will have approximately 99% power to detect a difference between the treatment groups of 5.0 percentage points for the absolute change in ppFEV1 from baseline through Week 24, based on a 2-sided, 2-sample *t*-test at a significance level of 0.05.

Another key secondary endpoint is the number of PEx through Week 24. Assuming a rate of PEx for the placebo group of 0.6 over 24 weeks and a 10% dropout rate, with 180 subjects and the overdispersion parameter of 0.5 in each treatment group, the power to detect a 40% reduction in the PEx rate for TC group compared to placebo group is approximately 80%, based on a 2-sided, 2-sample negative binomial regression model test for the ratio of rates, at a significance level of 0.05.

## 12.2 Analysis Sets

The following analysis sets are defined: All Subjects Set, Full Analysis Set (FAS), and Safety Set.

The **All Subjects Set** will include all subjects who were randomized or received at least 1 dose of study drug. This analysis set will be used for all individual subject data listings and disposition summary tables, unless otherwise specified.

The **FAS** will include all randomized subjects who carry the intended *CFTR* allele mutation and receive at least 1 dose of study drug. The FAS will be used to summarize subject demographics and baseline characteristics, and for all efficacy analyses in which subjects will be analyzed according to their randomized treatment group, unless otherwise specified.

The **Safety Set** will include all subjects who received at least 1 dose of study drug. The Safety Set will be used for all safety analyses in which subjects will be analyzed according to the treatment they received, unless otherwise specified.

Additional analysis sets related to the interim analysis will be described in the SAP.

## 12.3 Statistical Analysis

### 12.3.1 General Considerations

**Continuous variables** will be summarized using the following descriptive summary statistics: the number of subjects (n), mean, SD, median, minimum value (min), and maximum value (max). The precision of the measurement for each continuous variable will be specified in the SAP. Unless otherwise specified, min and max values will be reported with the same precision as the units of the raw data. The mean, median, and SD will be reported to 1 additional decimal place. Any values that require a transformation to standard units (metric or SI) will be converted with the appropriate precision.

**Categorical variables** will be summarized using counts and percentages. Percentages will be presented to 1 decimal place.

The **baseline value**, unless otherwise specified, will be defined as the most recent non-missing measurement (scheduled or unscheduled) collected before the first dose of study drug. For ECG, baseline will be defined as the most recent pretreatment measurement (or the average of triplicate measurements, if the most recent pretreatment measurement is obtained in triplicate) before the first dose of study drug.

**Absolute change** from baseline will be calculated as post-baseline value – baseline value.

The **Treatment-emergent (TE) Period** will include the time from the first dose of study drug in the Treatment Period (TC or Placebo) to 28 days after the last dose of the study drug or to the completion of study participation date (as defined in [Section 9.1.6](#)), whichever occurs first.

### 12.3.2 Background Characteristics

#### 12.3.2.1 Subject Disposition

The number and percentage of subjects in each disposition category (e.g., randomized, included in the FAS, included in the Safety Set, completed Treatment Period, completed study, prematurely discontinued treatment or study with a breakdown of the reasons for discontinuation, and entered an open-label study) will be summarized overall and by treatment group.

#### 12.3.2.2 Demographics and Baseline Characteristics

Demographic, medical history, and baseline characteristics will be summarized using descriptive summary statistics.

The following demographics and baseline characteristics will be summarized overall and by treatment group for the FAS and will include (but are not limited to): sex, race, baseline age, baseline weight, baseline height, baseline BMI, baseline ppFEV1, and baseline SwCl.

Medical history will be summarized by MedDRA System Organ Class (SOC) and Preferred Term (PT) for the FAS.

No statistical tests will be performed to evaluate baseline imbalance between treatment groups.

#### 12.3.2.3 Prior and Concomitant Medications

Medications will be coded using the World Health Organization Drug-Dictionary and categorized as follows:

- **Prior medication:** any medication that was administered during the 56 days before initial dosing of study drug
- **Concomitant medication:** medication continued or newly received during the TE Period
- **Post-treatment medication:** medication continued or newly received after the TE Period

A given medication may be classified as a prior medication, a concomitant medication, or a post-treatment medication; both prior and concomitant; both concomitant and post-treatment; or prior, concomitant, and post-treatment. If a medication has a missing or partially missing start/end date or time and if it cannot be determined whether it was taken before the first dose of study drug, concomitantly during the TE Period, or after the TE Period, it will be considered in all 3 categories of prior, concomitant, and post-treatment medication.

Prior medications and concomitant medications will be summarized descriptively by Preferred Name based on the FAS. Post-treatment medications will be provided separately in an individual subject data listing.

#### **12.3.2.4 Study Drug Exposure and Compliance**

Study drug exposure will be summarized overall and by treatment group, based on the Safety Set in terms of the duration of treatment a subject received (in days), defined as the last day – the first day of study drug plus 1, regardless of study drug interruption.

Study drug compliance will be summarized overall and by treatment group based on the FAS, and will be calculated as:  $100 \times [1 - (\text{total number of days of study drug interruption}) / (\text{duration of study drug exposure in days})]$ . A study drug interruption on a given day is defined as an interruption of any study drug on that day.

In addition, percentage of tablets taken will also be summarized overall and by treatment group based on the FAS, and will be calculated as  $100 \times [(\text{total number of tablets dispensed}) - (\text{total number of tablets returned})] / (\text{total number of tablets planned to be taken per day} \times \text{duration of study drug exposure in days})$ .

#### **12.3.2.5 Important Protocol Deviations**

An important protocol deviation (IPD) is a deviation that may significantly affect the completeness, accuracy, or reliability of the study data or that may significantly affect a subject's rights, safety, or well-being. The rules for identifying an IPD will be described in the SAP.

All IPDs will be provided in an individual subject data listing, and summarized, as appropriate.

### **12.3.3 Efficacy and Pharmacodynamic Analysis**

The primary objective of the study is the evaluation of the efficacy of VX-659 in TC with TEZ and IVA. The analyses described in this section will be based on the FAS, unless otherwise specified.

#### **12.3.3.1 Final Analysis**

##### **12.3.3.1.1 Analysis of Primary Variables**

The primary efficacy variable is the absolute change in ppFEV1 from baseline at Week 4. The analysis of this variable will be performed using a mixed-effects model for repeated measures (MMRM) with change from baseline at Day 15, Week 4, Week 8, Week 12, Week 16, and

Week 24 as the dependent variable. The model will include treatment group, visit, and treatment-by-visit interaction as fixed effects, with continuous baseline ppFEV1, age at screening (<18 versus ≥18 years of age) and sex (male versus female) as covariates. The model will be estimated using restricted maximum likelihood. Denominator degrees of freedom for the *F*-test for fixed effects will be estimated using the Kenward-Roger approximation. An unstructured covariance structure will be used to model the within-subject errors. If the model estimation does not converge, a compound symmetry covariance structure will be used instead. Conditional on the observed data and covariates, missing data will be assumed to be missing at random; consequently, no imputation of missing data will be performed.

The primary result obtained from the model will be the estimated treatment difference at Week 4. The adjusted mean difference at Week 4 with 2-sided 95% confidence intervals and 2-sided *P* values will be provided. Furthermore, the adjusted mean and treatment difference at each post-baseline visit will also be provided, obtained from the model.

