### **Unblinding: Interim Analysis**

The IA will be performed by an external independent biostatistician who is not involved in and will not influence study conduct. The analyses generated by the external independent biostatistician will then be reviewed by the IDMC. If the IDMC declares that the study has crossed the prespecified efficacy boundary ([Section 12.3.6.1](#)), then the study may be unblinded by a limited Vertex team to prepare a regulatory submission(s). Members of the limited Vertex unblinded team will not be involved in or influence the conduct of the remaining part of the

study to protect the integrity of the study. Regardless of the outcome of the IA, the study will continue through Week 24, and the subjects (and their parents/caregivers/companions), site personnel (including the investigator, the site monitor, and the study team), and members of the Vertex study team will remain blinded until the final database lock.

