#### 12.3.3.4 Multiplicity Adjustment

The Lan and DeMets alpha spending function will be applied to the primary endpoint of the absolute change in ppFEV1 at Week 4 to control the overall type I error rate of 0.05 such that an alpha of 0.01 will be preserved for the final analysis.

If the number of subjects included in the IA is 140, the primary endpoint of the absolute change from baseline in ppFEV1 at Week 4 will be tested at an alpha of 0.044 during the IA. The actual alpha at the IA ( $\alpha_0$ ) will be determined based on the actual number of subjects included in the IA. If the study does not cross the efficacy boundary during the IA (*P* value  $\geq \alpha_0$ ), then the primary endpoint will be tested at an alpha of 0.01 at the final analysis when all subjects complete study participation.

The key secondary endpoints will be formally tested at an alpha of 0.05 at the final analysis when all subjects complete study participation only if the primary endpoint is statistically significant at the IA or at the final analysis. A hierarchical testing procedure will be used to control the type I error rate for the multiple key secondary endpoints tested at an alpha of 0.05. For a test at any step to be considered statistically significant within the testing hierarchy, it must be statistically significant, and all previous tests (if any) within the hierarchy must be statistically significant at the 0.05 level. The testing order of the key secondary endpoints is as follows:

1. First key secondary endpoint: Absolute change in ppFEV1 from baseline through Week 24
2. Second key secondary endpoint: Number of PEx through Week 24

3. Third key secondary endpoint: Absolute change in SwCl from baseline through Week 24
4. Fourth key secondary endpoint: Absolute change in CFQ-R respiratory domain from baseline through Week 24
5. Fifth key secondary endpoint: Absolute change in BMI from baseline at Week 24
6. Sixth key secondary endpoint: Absolute change in SwCl from baseline at Week 4
7. Seventh key secondary endpoint: Absolute change in CFQ-R respiratory domain score from baseline at Week 4

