**Table 7-2 The Alpha Spending with Various N at the Interim Analysis**

Sample Size in interim Full Analysis Set (information fraction)	Alpha at IA ( $\alpha_0$ )	Alpha at Final ( $\alpha_1$ )
140 (39%)	0.0440	0.01
180 (50%)	0.0451	0.01
220 (61%)	0.0465	0.01
260 (72%)	0.0480	0.01
300 (83%)	0.0492	0.01

If the *P* value for the primary endpoint at the IA is less than  $\alpha_0$ , then the efficacy boundary has been crossed. If the DMC declares that the study has crossed the efficacy boundary, then the study may be unblinded to a limited Vertex team to prepare regulatory submission(s). Members of the limited Vertex unblinded team will not be involved in or influence the conduct of the remaining part of the study to protect the integrity of the study.

If the *P* value fails to cross the efficacy boundary during the IA (i.e., *P* value  $\geq \alpha_0$ ), then the primary endpoint of absolute change in ppFEV1 from baseline at Week 4 will be tested after all subjects complete study participation at an alpha of 0.01.

Selected key secondary endpoints will be analyzed during the IA with nominal *P* value provided for descriptive purpose (see Section 10.1.3.2).

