##### **9.3.1.2 Primary Analysis**

The primary analysis will be performed using a mixed-effects model for repeated measures (MMRM) with change from baseline at Day 15, Week 4, Week 8, Week 12, Week 16, and Week 24 as the dependent variable. The model will include treatment group, visit, and treatment by visit interaction as fixed effects, with continuous baseline ppFEV1, age at screening (<18 versus ≥18 years of age) and sex (male versus female) as covariates. The model will be estimated using restricted maximum likelihood. Denominator degrees of freedom for the *F*-test for fixed effects will be estimated using the Kenward-Roger approximation. An unstructured covariance structure will be used to model the within-subject errors. If the model estimation does not converge, a compound symmetry covariance structure will be used instead. Conditional on the observed data and covariates, missing data will be assumed to be missing at random; consequently, no imputation of missing data will be performed.

The primary result obtained from the model will be the estimated treatment difference at Week 4. The adjusted means with 2-sided 95% confidence intervals and 2-sided *P* values will be provided. Furthermore, the treatment difference at each post-baseline visit obtained from the model will also be provided.

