### 10.1 Interim Analysis

#### 10.1.1 General Consideration

Refer to Section 7.5 for the timing of the IA. General considerations, reporting conventions, and analysis methods specified for the final analysis apply to the IA, unless otherwise specified.

For the IA purpose, the **treatment-emergent (TE) period** will include the time from the first dose of study drug in the Treatment Period until 28 days after the last dose of study drug, or the study participation end date, or the IA data cutoff date, whichever occurs first.

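### Does an unadjusted 95% interval for the Week 4 difference conflict with tests at 0.044 and 0.01?

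*Protocol*

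**What the plan says.** **Tests.** Protocol 12.1 sets the primary test "at a 2-sided significance level of 0.044 during the IA and at an overall 2-sided significance level of 0.05", assuming 140 subjects at the interim. SAP Table 7-2 gives interim levels from 0.0440 (N=140) to 0.0492 (N=300), each paired with 0.01 at the final. If the interim does not cross, Protocol 12.3.3.4 says "then the primary endpoint will be tested at an alpha of 0.01 at the final analysis when all subjects complete study participation". SAP 7.5 agrees: the endpoint "will be tested after all subjects complete study participation at an alpha of 0.01".

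**Intervals.** Protocol 12.3.3.1.1 and the synopsis specify "The adjusted mean difference at Week 4 with 2-sided 95% confidence intervals". SAP 9.3.1.2 has "The adjusted means with 2-sided 95% confidence intervals", and SAP 9.3.2.2 adds 95% intervals for the treatment difference at each visit. No 99% interval, and none at the interim level, is visible.

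**Interim reporting.** SAP 10.1.1 says "reporting conventions, and analysis methods specified for the final analysis apply to the IA, unless otherwise specified". The lines after the model paragraph in SAP 10.1.3.1 are redacted. The interim is also run under a separate DMC SAP (SAP 4 and 10), which is not among the documents.

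**After a crossing.** Protocol 10.7.2: "Regardless of the outcome of the IA, the study will continue through Week 24". The same Week 4 difference is then estimated again on all data.

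**The concern.** The primary contrast is never tested at 0.05, yet its interval is a 95% one. Two awkward outcomes are possible.

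1. The interim fails and the final P lies between 0.01 and 0.05. The primary endpoint fails and the key secondary hierarchy stays closed, but the printed interval excludes zero. A reader may take that as success. If the 95% intervals were used as the tests at both looks, the two-sided error would be 8.7% instead of 5%.
2. The interim crosses, a submission may be prepared from it, and a second Week 4 interval follows at the final. No visible sentence says which of the two is the main one. If the 95% interval from whichever look decided the test were taken as the main one, its coverage with no true effect would be 91.8%.

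**Working it through.** **Inputs.** SD 7, planned difference 5.0, 5% dropout at Week 4, 70 per arm at the interim and 180 at the final (Protocol 12.1); interim levels and information fractions (SAP Table 7-2). Analysed per arm: 70 × 0.95 = 66.5 and 180 × 0.95 = 171. Normal approximation throughout; Z1 and Z2 are the interim and final test statistics.

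**1. The plan's own figures.** With correlation √(140/360) = 0.624 and a final cut of 2.576, solving P(|Z1| > c or |Z2| > 2.576) = 0.05 under no effect gives an interim level of 0.04395, which rounds to the stated 0.0440. The other four rows solve to 0.0452, 0.0466, 0.0479 and 0.0492, against 0.0451, 0.0465, 0.0480 and 0.0492 in the table. Interim power by t-test with 66.5 per arm is 98.1%, against about 98% stated. The testing scheme is sound.

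**2. Half-widths.**
- Interim SE = 7 × √(2/66.5) = 1.214. The 95% half-width is 1.960 × 1.214 = 2.38; at 95.6%, 2.014 × 1.214 = 2.45.
- Final SE = 7 × √(2/171) = 0.757. The 95% half-width is 1.960 × 0.757 = 1.48; at 99%, 2.576 × 0.757 = 1.95.

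Test and 95% interval therefore disagree for observed differences, in absolute value, of 2.38 to 2.45 points at the interim or 1.48 to 1.95 points at the final.

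**3. How often** (N=140, bivariate normal integration):

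| True difference | Interim P between 0.044 and 0.05 | Interim fails, final test fails, final 95% interval excludes 0 | Interim crosses, final 95% interval includes 0 |
|---|---|---|---|
| 0 | 0.6% | 3.2% | 3.2% |
| 1 | 1.1% | 12.3% | 3.9% |
| 2 | 2.0% | 17.5% | 2.0% |
| 3 | 1.9% | 4.6% | 0.2% |
| 5 (planned) | 0.2% | 0.002% | about 0 |

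The counts are two-sided. With no effect, half of the 3.2% in the middle column (1.6%) are intervals wholly above zero. With an interim at N=300, that column is 1.9% at 0 and 9.0% at 2 points.

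**4. Coverage.**
- Final all-data 95% interval: 95.0% at every true difference, since the final estimate is formed whether or not the interim crosses.
- 95% interval from the deciding look: 91.8%, 94.0%, 94.8% and 96.2% at 0, 1, 2 and 5 points.
- Intervals matched to the deciding test (95.6% or 99%): 95.0% at 0, and about 97% at 1 to 5 points.

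**5. What an interim-based main estimate would cost.** Given a crossing in favour of active, the mean interim estimate is δ + SE × φ(a)/(1 − Φ(a)), with a = 2.014 − δ/SE. For δ = 2: a = 2.014 − 2/1.214 = 0.367, and 2 + 1.214 × 0.373/0.357 = 3.27. For δ = 3 the same formula gives 3.65.

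**The case for a change.** The strongest case for acting is that the protocol calls the estimated Week 4 difference the primary result, so its interval should match the test that decides success. The final-analysis mismatch is in unredacted text. At true differences of 1 to 2 points it would appear in 12% to 18% of trials. Naming the main interval in advance costs a sentence and removes a choice made after both are known.

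The mismatch does stand, and so does the absence of a sentence on which interval leads after a crossing. Three things limit what follows:

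- No rule uses the interval. The alpha split is there "to control the overall type I error rate of 0.05", and success is always a P value against the interim level or 0.01.
- The visible text already leans one way. The Week 4 difference is called the primary result in Protocol 12.3.3.1.1, which sits under the final-analysis heading. SAP Section 9 is declared to cover the final analysis, and its 9.3.1.2 is the section titled as the primary analysis. The interim model is set out separately. The 91.8% coverage needs a reading that no section states.
- For the interim, redaction and the separate DMC SAP mean one cannot say that the plan is silent, only that the visible text is.

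Matching intervals to tests is a trade-off. After a crossing it would lead with a half-width of 2.45 instead of 1.48 points, around an estimate that averages 3.27 when the truth is 2. Two Week 4 intervals would still be reported, and they could still differ.

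**Conclusion.** The observation is right, but it concerns presentation and calls for no change. Followed as written, the plan holds the two-sided error at 5.0% and yields a final 95% interval with its nominal 95.0% coverage. A 95% interval for estimation beside a test at another level is ordinary practice, and an analyst facing a final P between 0.01 and 0.05 would note in the report that the interval does not decide the test. After a crossing, the all-data estimate is the natural one to lead with, and the interim interval supports the interim decision.

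At the planned 5 points, the final conflict has probability 0.002% and the interim one 0.2%. It becomes noticeable (12% to 18%) only at true effects of 1 to 2 points, well below design. These figures assume SD 7, 5% dropout at both looks, an interim at 140 of 360 and a normal approximation. The conclusion does not depend on their exact values, because no decision rests on the interval.
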